3.1.1 Rationale of Study Design

In prior clinical studies, GTx-024 has been generally well tolerated, including single doses up to 100 mg and multiple doses up to 30 mg once daily for up to 14 days. In longer studies, GTx-024 has also been generally well tolerated at 1, 3, and 9 mg daily doses for up to 833 days (GTx, Inc. 2017). The open-label extension study will provide additional long-term safety and tolerability data for GTx-024.

3.1.1.1 Risk Mitigation

This study has been designed to mitigate known risks associated with the use of GTx-024. Clinical study G200501 observed the effects of administering doses of 0.1, 0.3, 1, and 3 mg of GTx-024 (or placebo) for 86 days to healthy subjects: postmenopausal women and elderly men. Dose-dependent increases in serum alanine aminotransferase (ALT) and aspartate aminotransferase (AST) were observed. A higher incidence of transient, asymptomatic increases in ALT levels reported as AEs occurred in the group receiving GTx-024 3 mg (20.8%) compared with the placebo group (0%). One subject who received 3 mg/day of GTx-024 was discontinued due to an ALT level >3 times the upper limit of normal (ULN). The ALT levels returned to normal with continued exposure to GTx-024 in most cases and, furthermore, in instances when dosing was not continued, levels returned to normal. No significant increases in levels of total bilirubin, gamma glutamyl transferase, alkaline phosphatase, or lactate dehydrogenase have been observed in subjects with elevated ALT levels. Consistent with the effects of other orally administered anabolic agents, GTx-024 causes a dose-dependent reduction in high-density lipoprotein (HDL), the clinical significance of which is unknown at this time. The proposed mechanism for reduction in HDL is due to stimulation of reverse cholesterol transport and increased HDL catabolism by hepatic lipase. Reductions in HDL levels are temporary and typically return to baseline levels 12 months after treatment initiation.

In an ongoing, Phase 2 study of GTx-024 in estrogen receptor-positive/androgen receptor-positive breast cancer that is examining daily doses of GTx-024 at 9 and 18 mg, several cases of clinically significant hypercalcemia have been observed that were assessed by the investigators as possibly related to GTx-024. Subjects with hypercalcemia had

estrogen receptor–positive breast cancer with bone metastases. Hypercalcemia has not been observed in previous studies of healthy individuals or at doses <9 mg.

Subjects will be monitored at each visit for health changes since the previous visit and adverse effects of treatment. Since elevations in ALT levels have been observed in prior studies, serum ALT and other liver function analytes will be monitored at each visit during treatment (Table 12–1). Stopping rules have been included for severe elevations of liver function tests or other signs of hepatotoxicity (Section 6.3.2). Subjects will also be monitored for changes in lipid profile and serum calcium.

The effect of GTx-024 on a fetus has not been evaluated; therefore, the subjects in the current investigation will be postmenopausal.

4 Subject Selection and Withdrawal Criteria

4.1 Selection of Study Population

Up to 500 subjects will be enrolled at around 65 sites in the United States (US). Subjects will be enrolled in the current study only if they meet all of the inclusion criteria and none of the exclusion criteria.

Deviations from the inclusion and exclusion criteria are not allowed because they can potentially jeopardize the scientific integrity of the study, regulatory acceptability, or subject safety. Therefore, adherence to the criteria as specified in the protocol is essential.

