the atrophy in urethral muscle that was observed in the control group. This preliminary in vivo study supports the clinical study of SARMs for the treatment of SUI.

A proof-of-concept study is currently ongoing to investigate the effect of GTx-024 on symptoms of SUI in postmenopausal women. Available data from the 18 subjects who received doses of GTx-024 3 mg once daily for 12 weeks showed a mean reduction in stress incontinence episodes of 81%, with all 18 subjects experiencing clinically significant reduction ($\geq 50\%$ reduction in stress leaks) in the number of stress incontinence episodes by Week 12.

A double-blind, placebo-controlled, parallel-design, randomized, multicenter, Phase 2 study (G201002) is currently ongoing to assess the clinical activity and safety of GTx-024 in postmenopausal women with SUI. The study consists of a screening period (4 weeks), treatment period (12 weeks), follow-up period (4 weeks), and durability period (16 weeks).

The current 12-week, open-label extension study will enroll the following subjects from G201002:

- From the first 225 subjects enrolled in G201002, only subjects randomly assigned to the placebo group and who have completed the 12-week treatment period and 16-week durability period from G201002 will be allowed to enroll in this study, once data from G201002 are unblinded. Placebo subjects who enrolled in the durability extension study (G201003) will be allowed to discontinue participation in G201003, once data from G201002 have been unblinded
- From Subject 226 onwards, any subject who was randomly assigned to any treatment group and who has completed the 12-week treatment period and the 4-week follow-up period in Study G201002 will be allowed to enroll

This open-label extension study will provide additional long-term safety and tolerability data for GTx-024. All subjects in this study will receive GTx-024 3 mg orally, once daily.

2 Study Objectives

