3.1 Study Design

This is a multicenter, Phase 2, open-label extension study that will assess the long-term safety and tolerability of GTx-024.

The current study will enroll the following subjects from G201002:

- From the first 225 subjects enrolled in G201002, only subjects randomly assigned to the placebo group and who have completed the 12-week treatment period and 16-week durability period will be allowed to enroll in this study, once data from G201002 are unblinded. Placebo subjects who enrolled in the durability extension study (G201003) will be allowed to discontinue participation in G201003, once data from G201002 have been unblinded
- From Subject 226 onwards, any subject who was randomly assigned to any treatment group and who has completed the 12-week treatment period and the 4-week follow-up period in Study G201002

All subjects in this study will receive GTx-024 3 mg orally, once daily.

The study consists of the following visits:

Baseline (Day 0)

Subjects will be evaluated, and an additional written informed consent for the open-label extension study will be obtained. Procedures will be performed at baseline as specified in the schedule of events (Table 12–1) for the study.

Long-term Open-label Extension Period

Subjects who continue to meet the eligibility criteria will attend clinic visits at 4-week intervals for the first 12 weeks of the open-label extension study (i.e., Weeks, 4, 8, and 12). Following the first 12 weeks, subjects will attend clinic visits every 12 weeks (i.e., 12 weeks from Visit 3 onwards). At each clinic visit, study procedures will be performed as specified in the schedule of events (Table 12–1).

There is currently no planned end to this study; instead, subjects will be on treatment and followed until marketing approval is granted to GTx-024 or until the withdrawal of the Investigational New Drug application. If marketing approval is granted to GTx-024, a plan

for the transition of subjects from study drug to commercial drug product or other therapy will be implemented.

Data from this open-label extension study will be used to assess the long-term safety and tolerability of GTx-024.

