4.1.1 Inclusion Criteria

Each subject must meet all of the following criteria to be enrolled in this study:

1. Be an eligible subject from G201002, where an eligible subject is defined as:
 - a. one of the first 225 subjects who were randomly assigned to the placebo group in G201002 and who have completed the required treatment and durability periods of that study, or;
 - b. any subject from 226 onwards, who was randomly assigned to any treatment group and who completed the required treatment and follow-up periods of that study
2. Be able to read, understand, and provide written, dated informed consent prior to enrollment in the current study and be likely to comply with the study protocol and communicate with study personnel about AEs and other clinically important information
3. Provide written consent to participate in the study within the following timeframes:
 - a. for G201002 Subjects 1-225, within 30 days after the unblinding of G201002 (subjects who consent to participate in G201003 will be allowed to discontinue from that study and consent to this study upon unblinding of G201002)
 - b. for G201002 Subjects 226-493, within 30 days of completing both the treatment and follow-up period of G201002

4. Agree to maintain a stable dose of any medication known to affect lower urinary tract function, including but not limited to anticholinergics, tricyclic antidepressants, beta-3 adrenergic agonists, or α -adrenergic blockers, throughout the duration of the study

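### Does the enrolment cap of 500 need changing when the entry criteria can admit fewer than 493 women?

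*Combined protocol and SAP*

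**What the plan says.** Section 4.1 gives the only study size in the protocol: "Up to 500 subjects will be enrolled at around 65 sites in the United States (US". The same section says that a woman enters only if she meets every inclusion criterion and no exclusion criterion, and that deviations from the criteria are not allowed.

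Section 4.1.1, criterion 1 limits entry to the parent study: "Be an eligible subject from G201002, where an eligible subject is defined as" one of two groups. Section 3.1 describes the first group: "From the first 225 subjects enrolled in G201002, only subjects randomly assigned to the placebo group", and these women must also have completed the treatment and durability periods. The second group in criterion 1 is "any subject from 226 onwards, who was randomly assigned to any treatment group", again completers only. Criterion 3 then sets the consent windows. For the second group it reads "for G201002 Subjects 226-493, within 30 days of completing both the treatment and follow-up period of G201002", so the subject numbering stops at 493.

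Section 1.1 describes the parent: "A double-blind, placebo-controlled, parallel-design, randomized, multicenter, Phase 2 study (G201002) is currently ongoing". Some of its subjects were therefore randomised to active drug. The documents do not give the allocation ratio.

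Section 7.3 says that no power calculation was done because no formal analysis is planned. Section 7.6 plans descriptive summaries by visit, with 95% confidence intervals where appropriate. Section 4.2.3 rules out replacement of women who leave early.

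**The concern.** A closed source population fixes how large an extension study can be, and here the stated size is larger than the source. Even if every parent subject could enter, the count would stop at 493. The placebo-only rule for the first 225 then removes every woman in that block who was randomised to active drug, so the real ceiling is lower again.

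This would matter if 500 carried weight. The primary objective is long-term safety, and the number treated governs how well uncommon adverse events can be excluded. There is no sample-size rationale to fall back on and no replacement of withdrawals. A reader could take 500 as the planned size of the safety database, and so as a promise of precision that the criteria cannot deliver. One could also suspect that drug supply or ethics review was planned on it.

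**Working it through.** **Inputs from the documents.** Stated cap 500 (4.1). Last parent subject number 493 (4.1.1, criterion 3b). Placebo-only block: Subjects 1 to 225 (3.1; 4.1.1, criteria 1a and 3a). Any-arm block: Subjects 226 to 493. Placebo-controlled randomised parent (1.1).

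**Assumed, not in the documents.** Placebo share p in the parent, taken as 1/2, 1/3 and 1/4, with 1/5 as a further case. Where used below, rollover of 70% to 85%.

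**Step 1: where 500 may come from.** The any-arm block is 493 − 226 + 1 = 268. Ignoring treatment arm, the parent total is 225 + 268 = 493. That is 7 below 500, or 7/500 = 1.4%. The cap looks like the parent total rounded up, although the protocol does not say so.

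**Step 2: ceiling under the actual criteria.** Ceiling = 268 + (placebo women among Subjects 1 to 225). Reaching 500 would need 500 − 268 = 232 placebo women out of 225, which is impossible. Because the parent has at least one active arm, the ceiling is strictly below 268 + 225 = 493. It is above 268 as long as any of the first 225 were on placebo.

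**Step 3: size of the gap under assumed allocations.** Ceiling = 268 + 225p.

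| Assumed placebo share | 225p | Ceiling | Below 500 |
|---|---|---|---|
| 1/2 | 112.5 | about 380 | 24% |
| 1/3 | 75 | 343 | 31% |
| 1/4 | 56.25 | about 324 | 35% |
| 1/5 | 45 | 313 | 37% |

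These are maxima, before non-completion of the parent, exclusions, refusals and missed consent windows.

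**Step 4: effect on what the safety data could exclude.** If an adverse event is never seen in n women, the one-sided 95% upper bound on its incidence is 1 − 0.05^(1/n).

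- n = 500: 0.60%
- n = 380: 0.79%
- n = 343: 0.87%
- n = 324: 0.92%
- n = 292 (85% of 343): 1.02%
- n = 240 (70% of 343): 1.24%

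From 500 to 343 the bound moves by 0.87 − 0.60 = 0.27 percentage points.

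**Step 5: does anything in the plan use 500?**

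- Section 7.3 and the synopsis entry on sample size give no number.
- Section 7.4 defines the safety set as women who received at least one dose.
- Section 7.6.1 bases adverse-event percentages on women who received treatment. Denominators and interval widths therefore come from actual enrolment.
- Section 6.3.2 states its halting rules per subject, with no study-level event count or rate.
- Section 5.4 promises adequate drug supply without a headcount.
- Section 8.1 on ethics review mentions no sample size.

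No calculation or rule takes 500 as an input.

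**The case for a change.** The strongest case for a change is that a cap no enrolment could reach tells the reader nothing, and this cap is the only size the protocol offers. The primary objective is safety, so the number treated is the main determinant of what can be excluded, and the protocol could state the achievable number at no cost.

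Nor can the criteria be read so as to rescue the figure. Criterion 1b is open-ended ("any subject from 226 onwards, who was randomly assigned to any treatment group"), but criterion 3b provides no consent window beyond Subject 493. Criterion 1a, taken alone, might be read as the first 225 placebo subjects, but Section 3.1 makes clear that it means placebo subjects among the first 225 enrolled.

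The mismatch between 4.1 and 4.1.1 therefore stands, and so does the arithmetic in steps 1 and 2. The consequences do not. An unreachable target or powered sample size would be a defect, whereas an upper limit above the available pool contradicts no criterion. The plan claims no ability to detect uncommon events, so none is overstated. The documents do not link 500 to drug supply or ethics review, so harm there is conjecture. A headcount at entry also measures only part of long-term safety information in a study with no fixed end, where duration of exposure and retention matter as well. Adding a precision statement to 7.3, or expected numbers by prior treatment, would be new content for a descriptive extension that plans no subgroup analyses. It would not correct an error.

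**Conclusion.** The cap in Section 4.1 is a clerical slip: a loose upper limit, probably the parent total rounded up, that exceeds the pool defined in Sections 3.1 and 4.1.1. What the documents establish without assumption is that the ceiling is 268 plus the placebo women among Subjects 1 to 225, hence fewer than 493. The 24% to 35% shortfall rests on assumed placebo shares of 1/2 to 1/4 and widens to 37% at 1/5. The bounds of 1.02% and 1.24% rest in addition on an assumed rollover.

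No change to the plan follows. Enrolling 343 women, or 240, complies with a limit of 500. The entry criteria settle who is treated, and every summary uses the number actually treated. Restating the cap would leave eligibility, conduct, analysis and conclusions as they are. If the protocol is amended for another reason, the two sections could be brought into line then. This point alone does not justify an amendment.

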4.1.1 Inclusion Criteria

Each subject must meet all of the following criteria to be enrolled in this study:

1. Be an eligible subject from G201002, where an eligible subject is defined as:
 - a. one of the first 225 subjects who were randomly assigned to the placebo group in G201002 and who have completed the required treatment and durability periods of that study, or;
 - b. any subject from 226 onwards, who was randomly assigned to any treatment group and who completed the required treatment and follow-up periods of that study
2. Be able to read, understand, and provide written, dated informed consent prior to enrollment in the current study and be likely to comply with the study protocol and communicate with study personnel about AEs and other clinically important information
3. Provide written consent to participate in the study within the following timeframes:
 - a. for G201002 Subjects 1-225, within 30 days after the unblinding of G201002 (subjects who consent to participate in G201003 will be allowed to discontinue from that study and consent to this study upon unblinding of G201002)
 - b. for G201002 Subjects 226-493, within 30 days of completing both the treatment and follow-up period of G201002

4. Agree to maintain a stable dose of any medication known to affect lower urinary tract function, including but not limited to anticholinergics, tricyclic antidepressants, beta-3 adrenergic agonists, or α -adrenergic blockers, throughout the duration of the study

4.1.2 Exclusion Criteria

A subject who meets any of the following criteria will be excluded from the study:

1. Starts any new treatment (medication, pelvic floor physical therapy, or other treatment known to impact the pelvic floor) after completing G201002 that is known or suspected to affect lower urinary tract function, including vaginal rejuvenation
2. Subject is currently taking systemic sex-hormone products (excludes intravaginal application of estradiol topical/tablet agents and hormones delivered via vaginal rings). The following washout periods are required if systemic hormonal products are discontinued prior to screening:
 - a. minimum of 4 weeks for prior transdermal products or products with systemic absorption applied topically;
 - b. minimum of 8 weeks for prior oral products;
 - c. minimum of 8 weeks for prior intrauterine products, and;
 - d. minimum of 3 months for prior hormonal implants or injectable drug therapy.
3. Has a current cancer diagnosis (with the exception of nonmelanoma skin cancer) or any history of breast or endometrial cancer
4. Has a known history or current episode of:
 - a. New York Heart Association Stage ≥ 2 hypertension (systolic blood pressure > 160 mmHg or diastolic blood pressure > 100 mmHg) at screening and/or baseline. Subjects with hypertension that has been treated and controlled with medication for ≥ 2 weeks prior to screening are eligible for participation
 - b. Recent myocardial infarction or arterial or venous thromboembolic event (within 1 year) or a history of more than 1 myocardial infarction or arterial or venous thromboembolic event
 - c. Cardiac-related syncopal event within the past year

- d. Cardio or cerebral vascular disease requiring surgical intervention (e.g., bypass surgery, angioplasty). For subjects with previous stent placement, please contact the medical monitor
- e. Congestive heart failure of Stage > 2 according to New York Heart Association criteria
- f. Angina pectoris

5. Has a current or past history of any physical condition that, in the investigator's opinion, might put the subject at risk, impact absorption of the study drug, or interfere with interpretation of study results

4.2 Withdrawal of Subjects from the Study

The duration of the study is not fixed and is defined for each subject as the date signed, written informed consent is provided through the last follow-up visit depending on the commercial availability of GTx-024.

4.2.1 Reasons for Withdrawal/Discontinuation

Subjects are free to withdraw from the study at any time for any reason.

In addition, subjects may be withdrawn from the study by the principal investigator in consultation with GTx, Inc. for any of the following reasons:

- AEs that require treatment with a prohibited medication or procedure
- Development of any condition that may pose an additional risk to the subject or if the principal investigator decides it is in the best interest of the subject to withdraw from the study
- Sponsor's decision
- Subject is unable to follow investigators' instructions and/or to comply with the study procedures
- Protocol deviation
- Disease progression

The clinical study report will include reasons for all subject withdrawals from treatment as well as details relevant to violations of study prohibitions and concomitant therapy.

4.2.2 Handling of Withdrawals

Subjects are free to withdraw from the study or study treatment at any time upon request.

Subject participation in the study may be stopped at any time at the discretion of the investigator or at the request of the Sponsor.

Subjects who discontinue study treatment or active participation in the study will no longer receive GTx-024 and will be considered to have withdrawn from the study. When a subject withdraws from the study, the reason(s) for withdrawal shall be recorded by the investigator on the relevant page of the electronic case report form (eCRF). Subjects who discontinue from study drug will be monitored for AEs for 30 days after they stop treatment with study drug. Every effort will be made to obtain all end-of-treatment measures as outlined in Table 12-1, in the event that a subject withdraws, or is withdrawn, from the study before transitioning to commercial product or other therapy. Subjects who are not returning for final assessments will be contacted (2 documented telephone calls followed by 1 registered letter) by the site in an attempt to improve their compliance.

It is vital to obtain follow-up data on any subject withdrawn because of an AE or serious AE (SAE). In every case, efforts must be made to undertake protocol-specified, safety follow-up procedures. All data collected from all subjects, including early withdrawals and early discontinuations of treatment, will be used in the reporting and analysis of the study.

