6.1.3 Study Visit 4 Onwards: Week 24 Onwards, Clinic Visit

During the long-term safety period (after Visit 3), the subject will return to the study site for clinic visits. Concomitant medications and AEs will be reviewed. Weight and vital signs will be measured. Blood will be drawn for a CMP, CBC, and lipid panel. Completion of a 3-day voiding diary will be verified.

The hormone panel and SHBG tests will be assessed every 24 weeks only (i.e., every other clinic visit).

A transvaginal ultrasound examination will be performed every 24 weeks (i.e., every other clinic visit) in subjects with an intact uterus. Study drug will be dispensed, with administration instructions, at each clinic visit. The medication identification number assigned to the subject will be noted in the eCRF for study drug accountability. The subject will be reminded to bring all unused study drug (in its original packaging) to her next clinic visit.

The subject will be provided with a new 3-day voiding diary and instructed to complete it within the week preceding her next study visit.

Any subject who prematurely discontinues study or study drug will be asked to return to the study site and complete the end-of-study assessments.

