6.1.4 End-of-Study Visit

Approximately 30 days after the last dose of GTx-024, the subject will return to the study site for an end-of-study clinic visit. Unused study drug will be collected. Concomitant medications and AEs will be reviewed. Weight and vital signs will be measured. Blood will be drawn for a CMP, CBC, lipid panel, hormone panel, and SHBG test. Completion of a 3-day voiding diary will be verified.

The subject will complete the PGI-S and PGI-I questionnaires.

The subject will be instructed on the transition to commercial drug or other therapy by the physician.

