7.6 Statistical Analysis Methodology

A separate SAP will be finalized, providing detailed methods for all endpoints. In general, descriptive or summary statistics (n, mean, standard deviation, median, minimum and maximum values for continuous variables, and number [%] of subjects in each category for categorical variable) will be provided by visit. Source data for summary tables and statistical analyses will be presented as subject data listings.

All statistical analyses will be performed using SAS (version 9.3 or higher). No formal statistical analysis will be performed, as the open-label extension study is not powered for inferential statistics. Two-sided 95% confidence intervals will be provided where appropriate. No imputation will be done for missing data. The SAP will specify up to which visit summaries will be produced, as not all subjects will have been in the study for the same length of time. Further details on the analysis of efficacy endpoints will be provided in the SAP.

The study period is defined as baseline (Day 0) through end of study. Change from baseline will be between baseline (Day 0) and scheduled visits.

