7.6.1 Analysis of Safety Endpoints

All safety parameters (including AEs, vital signs, laboratory evaluations, SHBG, testosterone, and endometrial stripe thickness) will be summarized using the SAS set. No formal hypothesis testing will be performed.

All AEs will be coded using the latest version of MedDRA. All treatment-emergent AEs will be summarized and presented in the listings by the number of subjects who report an event, the percentage of subjects with that event, the number of events, and the grade, duration, and relationship to treatment. Percentages will be based on the number of subjects who received each treatment during the study.

Clinical laboratory safety tests will be performed, and normal ranges will be provided for each laboratory test. Values outside the normal range will be assessed for clinical significance by the investigator. Shift tables (change from baseline value to on-treatment values) will be presented for each laboratory measurement and assessment time. Each parameter outside the normal range will be designated as high (H) or low (L) in the individual data listings.

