12.1 Appendix: Schedule of Events

Table 12–1 Schedule of Events for Protocol G201004

Procedure	Baseline Day 0	V1	V2	V3	Long-term Safety	End of Study
Day or Week	Week 0	Week 4	Week 8	Week 12	Every 12 weeks following V3	30 days after last dose of GTx-024
Visit Window (days)	–	±7	±7	±7	±7	±7
Informed consent	X					
Eligibility criteria review	X					
Medical history	X					
Concomitant medications	X	X	X	X	X	X
Height ^a and weight	X	X	X	X	X	X
Vital signs	X	X	X	X	X	X
3-Day voiding diary	X	X	X	X	X	X
PGI-S	X	X	X	X	X	X
PGI-I		X	X	X	X	X
Adverse event reviews	X	X	X	X	X	X
CMP (Chem 16 panel)	X	X	X	X	X	X
CBC	X	X	X	X	X	X
Lipid panel	X	X	X	X	X	X
Hormone panel ^b	X	X	X	X	X	X
SHBG ^b	X	X	X	X	X	X
Transvaginal ultrasound ^c	X			X	X	
Dispense study drug	X	X	X	X	X	
Collect unused study drug		X	X	X	X	X

Abbreviations: CBC, complete blood count; CMP, comprehensive metabolic panel; PGI-I, Patient Global Impression of Improvement scale; PGI-S, Patient Global Impression of Severity scale; SHBG, sex hormone-binding globulin; V, visit.

^a Height is measured at baseline only.

^b During the long-term safety period, the hormone panel and SHBG will be assessed every 24 weeks only (i.e., every other clinic visit).

^c During the long-term safety period, the transvaginal ultrasound will be assessed every 24 weeks only (i.e., every other clinic visit)

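### Section 4.2.2 relies on end-of-treatment measures that Table 12-1 does not schedule; the only final visit is 23–37 days off drug, and no table summarises each woman's worst or last on-treatment laboratory value

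*Combined protocol and SAP*

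**What the plan says.** **Collection at withdrawal.** Section 4.2.2 states: "Every effort will be made to obtain all end-of-treatment measures as outlined in Table 12-1". Table 12-1 lists Baseline, V1 to V3, a Long-term Safety column ("Every 12 weeks following V3") and End of Study, timed "30 days after last dose of GTx-024" with a window of ±7 days.

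Section 6.1.3 says: "Any subject who prematurely discontinues study or study drug will be asked to return to the study site and complete the end-of-study assessments". Section 6.1.1 says the same in substance, and Section 6.1.4 sets the timing: "Approximately 30 days after the last dose of GTx-024, the subject will return to the study site for an end-of-study clinic visit".

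**Analysis.** Section 7.6 plans descriptive summaries by visit, without imputation, over a study period from Day 0 to end of study. It adds: "Change from baseline will be between baseline (Day 0) and scheduled visits". For laboratory data, Section 7.6.1 says: "Shift tables (change from baseline value to on-treatment values) will be presented for each laboratory measurement and assessment time". Further detail is left to a separate SAP that is still to be finalized.

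**Background.** Section 3.1.1.1 describes transient ALT rises at 3 mg, reported as adverse events in 20.8% of that group against 0% on placebo. Most resolved on continued dosing, and "in instances when dosing was not continued, levels returned to normal". Change in laboratory values is one of the primary safety measures (Sections 2.1 and 7.1).

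**The concern.** A site reading Section 4.2.2 would look in Table 12-1 for assessments tied to the end of treatment and find none. The visit it does find comes about a month after the drug has stopped. Section 4.2.2 itself stresses the importance of follow-up data on women withdrawn for adverse events, so the section is ambiguous where it matters most.

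The analysis text has a matching gap. No on-treatment window is defined for laboratory, vital-sign or efficacy data. The only post-dose window is the 30 days in the definition of a treatment-emergent adverse event (Section 6.3.1.1). Summaries are tied to scheduled visits, so a laboratory abnormality that comes and goes between visits, or is found at an unscheduled test, has no clear place in any summary table. At stake is how completely the report describes on-drug laboratory changes, above all in women who stop early.

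**Working it through.** The plan states no figure for this point, so there is nothing to reproduce. The check uses the visit timings and a side-by-side reading of the sections.

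**1. Is there an end-of-treatment visit?** The columns of Table 12-1 are Baseline, Weeks 4, 8 and 12, Long-term Safety, and End of Study. None is an end-of-treatment or early-termination visit, so the reference in Section 4.2.2 has no matching column.

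**2. Time off drug at the final visit** (Table 12-1: 30 days, ±7):
- 30 − 7 = 23 days; 30 + 7 = 37 days.
- Under a 30-day rule borrowed from the adverse-event definition, a visit on days 23–30 would count as on-treatment and one on days 31–37 would not. The same scheduled visit would be split by chance of booking.

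**3. Age of the last scheduled on-drug laboratory value at stopping** (Table 12-1: visits every 4 weeks to Week 12, then every 12 weeks, each ±7 days):
- Before Week 12: spacing 4 × 7 = 28 days, or 28 ± 14 = 14 to 42 with opposite windows.
- After Week 12: spacing 12 × 7 = 84 days, or 84 ± 14 = 70 to 98.
- A woman who stops just before a visit after Week 12 therefore has a last value up to 84 days old, or 98 at the extreme. If stopping times were uniform between visits (an assumption), the average would be 84 / 2 = 42 days. It would be shorter if stops cluster at visits.
- Hormone panel and SHBG in the long-term period: every 24 weeks, 24 × 7 = 168 days, or 168 ± 14 = 154 to 182.
- Transvaginal ultrasound follows the same 24-week pattern and is not marked at End of Study.

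**4. Stopping before the first post-baseline visit.** V1 is at Day 28 and its window opens at 28 − 7 = Day 21. Section 4.2.2 treats a woman who stops drug as withdrawn. If she stops before attending V1, her scheduled laboratory values are baseline and End of Study only. Her only post-baseline diary may also be off drug, yet one such diary satisfies the post-baseline requirement of the full analysis set (Section 7.4).

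**5. Where would End of Study values appear?**
- By-visit change from baseline (Section 7.6): End of Study is a scheduled column, so it would form its own row. Rows for Weeks 4, 8, 12, 24 and later do not change.
- Shift tables (Section 7.6.1): the restriction to on-treatment values points to leaving it out; the reference to every assessment time points to keeping it in. The text does not settle which.

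**6. What do by-visit tables miss?** Section 6.3.2 calls for an unscheduled visit when ALT or AST exceeds 3 × ULN, and for follow-up of discontinued women until abnormal values normalise. Section 6.6 lets the investigator repeat the metabolic panel. The resulting values are not at scheduled visits, so the change-from-baseline rule in Section 7.6 does not pick them up. Separate rows by visit also do not give the number of women who were ever abnormal on drug: different women at Weeks 4 and 8, or the same woman twice, can give identical rows.

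**The case against.** **Dilution is not shown.** A reader might infer that the off-drug visit feeds the on-treatment shift tables, waters down laboratory shifts and mixes loss of effect into the efficacy summaries. The documents do not support that. Section 7.6.1 names on-treatment values, which read literally excludes a visit 30 days after the last dose. Section 4.2.2 says that data from withdrawals will be used, but not in which table. Summaries are by visit, nothing is imputed or carried forward, and no pooled last-value table is planned. This objection stands in full.

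**Other safeguards exist.** The metabolic panel is drawn at every on-treatment visit, marked ALT or AST rises trigger an unscheduled visit, clinically significant abnormalities become adverse events, and treatment-emergent events are counted to 30 days after stopping. Adverse-event incidence does not depend on the final laboratory row. This stands too, but it covers events judged clinically significant. It does not put unscheduled laboratory values into a shift or change table.

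**The ALT history cuts both ways.** Most rises resolved on continued drug, and no recovery time after stopping is given. A normal End of Study value is therefore not proof of washout, and resolution by days 23–37 is an assumption. The same history supports a worst-value summary, because it describes rises that pass between visits.

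**It may be a slip, and detail is deferred.** End-of-treatment in Section 4.2.2 may simply mean end-of-study, and the separate SAP may define the window. Both are plausible. The wording still needs to agree, and the protocol gives the SAP no rule to follow.

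**Conclusion.** The concern holds in limited form. It is certain that Section 4.2.2 refers to measures Table 12-1 does not contain, and that the only final visit falls 23–37 days off drug. It follows from the visit spacing that a woman stopping after Week 12 may have a last scheduled on-drug laboratory value up to 84 days old (98 with windows), and that one stopping before V1 may have no scheduled on-drug value at all.

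For the analysis, the risk is an off-drug row labelled or read as on-treatment, together with transient on-drug laboratory changes left out of the summaries. The size of that loss cannot be computed: the documents give neither the share of women expected to stop early nor the time to laboratory recovery. No stated figure changes, and nothing shows that results at other visits would be distorted. In a descriptive, single-arm study this calls for reconciled wording and an inexpensive improvement to the tables; it is not a flaw in the design.

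**What to change.** 1. Reconcile Sections 4.2.2, 6.1.1, 6.1.3 and 6.1.4 with Table 12-1 on which assessments early stoppers have and when, using one term throughout. Cost: protocol wording.
2. In Sections 7.6 and 7.6.1, and in the SAP, define the on-treatment window for laboratory, vital-sign and efficacy data, and report End of Study separately as off-treatment. Cost: a definition and a row label.
3. In Section 7.6.1, add shift and change-from-baseline tables for each woman's worst and last on-treatment laboratory values, including unscheduled tests. State the direction of worst for each parameter (for example, highest for ALT, lowest for HDL). Cost: a few extra tables from data already collected.

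Items 2 and 3 need no added visit. They do not shorten the gaps between visits; they make clear what was measured on drug and what was not.
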